4.1.5 Administrative Structure

In order to keep the study personnel blinded during interim analyses, an Internal Monitoring Committee (IMC) will be established.

The unblinded IMC will review the results of each interim analysis and recommend to the study team whether the study should stop, continue, or be modified.

The IMC is a dedicated group of selected Sponsor representatives, who will be independent from the project and review the safety and efficacy data of the study, as well as the interim analyses. The roles, responsibilities, membership, scope of activities, time of meetings, and communication plan for the IMC will be documented in an appropriate charter.

4.2 SCIENTIFIC RATIONALE FOR STUDY DESIGN

The study rationale is provided in Section [2.1](#).

4.2.1 Rationale for Study Population

AIH is a rare and chronic disease without approved treatment. SoC consists of CCSs +/- NSIs. Untreated, the disease leads to death within 10 years of diagnosis mainly due to liver cirrhosis. Treatment with SoC enables patients with AIH to lead a nearly normal life with a normal life expectancy ([Heneghan et al 2013](#)).

Nevertheless, lifelong CCS/immunosuppressant treatment poses considerable burden on patients with AIH, sometimes with severe side effects like osteoporosis, muscle wasting, skin manifestations, and endocrine effects like steroid-induced diabetes ([Heneghan et al 2013](#)).

Treatment guidelines ([EASL 2015](#)) therefore recommend tapering patients off CCS treatment and (if possible) other immunosuppressive treatment, in order to relieve treatment-related side effects once the patients have reached biochemical remission and the liver shows no sign of inflammation. Withdrawal of SoC unfortunately leads more often than not to disease relapse (i.e., > 80% as reported by [van Gerven et al. 2013](#)). Relapsing patients will usually respond again to CCS treatment, require (in most cases) a higher dose, and have a longer duration to response ([van Gerven et al. 2013](#)). After the second relapse, it is recommended to keep patients on lifelong immunosuppressive treatment.

This study is conducted in patients with AIH currently on immunosuppressive treatment prior to their first attempt to taper CCS/NSIs completely *within the last 3 years* and who have an unmet medical need for a treatment option beyond CCSs/NSIs.

4.2.2 Rationale for Control Arm

RO7049665 will be compared with placebo, with participants randomized in a 1:1:1 ratio to receive one of two doses of RO7049665 or placebo. We will employ a blinded placebo arm to derive a preliminary assessment of the efficacy of the different doses of RO7049665 in participants with AIH in stable remission and for establishing drug-relatedness of AEs. A placebo arm will similarly inform the analysis of key biomarkers. As we are studying participants with a well-controlled but chronic disease, it will be critical to distinguish disease-related complications from intervention associated safety signals, as well as study treatment-related changes in leukocyte and cytokine biomarkers. In order to get a fair understanding of the efficacy of RO7049665 in AIH, it is important to establish the effect over placebo (i.e., to rule out a placebo effect).

Current *EASL* treatment guidelines ([EASL 2015](#)) propose withdrawal of CCS treatment once stable biochemical remission of more than two years without signs of inflammation ($\text{HAI} \leq 3$) has been achieved in order to remove the risk of CCS-related AEs. There is no approved treatment for patients with AIH following withdrawal of CCSs, and RO7049665 is an investigational drug with no established benefit. Therefore, placebo is an appropriate control treatment. Placebo injections are used purely to preserve the blind.

4.2.3 Rationale for Biomarker Assessments

Key objectives of the mandatory biomarker strategy are to:

- confirm and further investigate the expected effect of drug on target cells (expansion of T_{regs} in number)
- identify a safe dose at which the target PD effect can be observed
- confirm the magnitude and kinetics of this effect after multiple dosing and in the particular study population
- correlate a PD effect with clinical outcome

- characterize the expected target PD effects
- monitor biomarkers for unwanted events such as expansion of effector cells (T_{eff} cells, NK cells, and eosinophils)

These assessments are expected to add valuable information towards an estimate of the therapeutic window, patient selection, and prediction of clinical response.

Additional objectives of the mandatory biomarker assessments are: (1) to investigate if systemic PD effects can be measured as surrogate markers for predicting relapse; (2) to identify which of the candidate systemic biomarkers shows highest correlation to tissue effects (as available); (3) to determine if any systemic or tissue biomarkers can predict efficacy.

A fresh or historical liver biopsy is required before randomization. Provided no worsening of disease has occurred, a historical biopsy taken no more than 12 months prior to randomization is acceptable. A formalin-fixed paraffin embedded (FFPE) block has to be sent to the Sponsor if available. It will be used to characterize immune cell infiltration and histologic appearance. Additional measurements which may be performed on liver biopsy-derived material are whole (spatial) transcriptome or targeted gene expression analyses. An optional liver biopsy at 6 months of treatment will provide the opportunity to assess changes in tissue markers from baseline. The objective of these measurements is to confirm the translation of changes in T cell subsets from blood to tissue and to identify further mechanistic markers such as changes in inflammatory signatures or markers of tissue healing.

Blood samples will be collected to quantify relative and absolute WBC counts (including B cells, T cells, NK cells, and eosinophils). Furthermore, markers for quantification and characterization of T_{regs} and T_{eff} subsets including, but not limited to CD3, CD4, CD8, CD127, CD25, and FoxP3 will be determined.

Serum and plasma samples will be collected to measure cytokines or other soluble biomarkers mechanistically linked to RO7049665's mode of action or the disease. In addition, exploratory safety biomarkers may be measured in an ad-hoc fashion, (e.g., in participants experiencing symptoms associated with injection-related reactions).

Clinical blood genotyping data may be used to explore whether genotype may correlate with efficacy, influence the magnitude of PD effects, or impact the safety of RO7049665.

Exploratory disease biomarkers in serum samples will be tested for their ability to stratify participants and to evaluate their potential for non-invasive response to treatment monitoring.

Additional PD biomarkers and methods to obtain further confidence on the mechanism of action of RO7049665 in participants may be tested. Such assessments may include, but are not limited to, determining specific methylation signatures in blood or liver

biopsies to quantify T_{reg} or T_{eff} subsets and possibly the functionality of such. The purpose of this assessment is to explore alternative T cell subset quantification methods and to understand their potential usefulness for replacing established methods with limited throughput and logistical challenges in later stages of clinical development.

4.3 JUSTIFICATION FOR DOSE

The doses are based on data from the EIH study (WP39826) in healthy volunteers and the ongoing MAD WP40161 study in participants with UC. The therapeutic range of RO7049665 is unknown; however, the estimated therapeutic range of T_{reg} was achieved with the doses of 2200 µg, 5000 µg, and 7500 µg, eliciting a mean increase of 2-, 4-, and 6-fold, respectively, as compared with baseline without stimulating expansion of effector T cells (T_{eff}; see the [RO7049665 Investigator Brochure](#)). In AIH, the intrahepatic T_{reg}/T_{eff} ratio appears to be a determinant of disease progression, because patients reaching biochemical remission have higher intrahepatic T_{reg}/CD8 and T_{reg}/B cell ratios, whereas this ratio remains constant in the liver of untreated patients with AIH ([Taubert et al. 2014](#)). Also, the disproportional decrease of intrahepatic T_{reg} during SoC immunosuppressive therapy might explain the high relapse rates after discontinuation of immunosuppression. Thus, intrahepatic immunoregulation through T_{reg} expansion may be better suited for long-term control of AIH.

Data from WP39826 demonstrated 4-fold expansion of T_{reg} cells in healthy volunteers after a single 5-mg dose of RO7049665 (mean peak T_{reg} expansion to 155.2 cells/µL) and a mean 5.8-fold expansion of T_{reg} cells after a single 7.5-mg dose (with a mean peak of approximately 200 cells/µL [range 123 – 297]). The 2.2 mg single dose in the SAD study elicited a mean 2-fold increase in T_{reg} cells; therefore, the lower dose of 3.5 mg in Study BP42698 is expected to produce a measurable PD effect (specifically, the expansion of T_{reg} cells), but the overall expansion is projected to be at the lower end of the hypothesized therapeutic target.

Single doses at these dose levels were safe and well tolerated in healthy volunteers with no SAEs and no DLAEs, with limited expansion of T_{eff} and eosinophils and no observed effect on NK cells. The maximum T_{reg} expansion was observed at Day 8 following dosing. Similar results could be preliminarily confirmed in the MAD study WP40161.

Further details are provided in the [RO7049665 Investigator's Brochure](#).

4.4 END OF STUDY DEFINITION

The goal of the study is achieved when any of the interim analyses results in a decision to stop the study, when the required number of events is reached, or if any of the stopping rules apply. At this point, the study will be unblinded.

An individual participant has completed the study if he/she has completed all scheduled procedures as shown in the SoA (see Section 1.3).

The end of the study is defined as the date when the last participant last observation (LPLO) occurs. LPLO is expected to occur approximately 4 weeks after study closure when the final follow-up visit is conducted. Study closure can occur either after:

- The first interim analysis for futility, or
- The second interim analysis for futility or efficacy, or
- 45 events are observed, or
- Early study termination.

The Sponsor may set up an OLE study if RO7049665 development continues. Participants not having had a relapse at study closure may have the option to enter the OLE study. For participants entering a possibly available OLE study, the last regular visit will count as last observation in Study BP42698. Participants not entering the OLE study will have a last observation 4 weeks after the last dose of RO7049665 or placebo.

5. STUDY POPULATION

The study population rationale is provided in Section [4.2.1](#).

The participants of this study are patients with biopsy-proven diagnosis of AIH, with no evidence of cirrhosis with significant impairment of liver function stage (e.g., Child Pugh B or C). Patients must be in biochemical remission for at least 2 years (*or less if according to the local practice*), be on stable treatment (CCSs \pm NSIs) for at least 3 months prior to *randomization* (and who have not had a dose increase 6 months prior to *randomization*), and show no signs of inflammation (HAI \leq 3) on a liver biopsy taken no more than 12 months prior to randomization.

This study will recruit approximately 84 female and male participants diagnosed with AIH who are between 18 and 75 years of age, inclusive, and satisfy all of the inclusion and exclusion criteria.

Prospective approval of protocol deviations, also known as protocol waivers or exemptions, is not permitted.

5.1 INCLUSION CRITERIA

Participants are eligible to be included in the study only if all of the following criteria apply:

Informed Consent

1. Able and willing to provide written informed consent and to comply with the study protocol according to International Conference on Harmonisation (ICH) and local regulations.

Age

2. Between 18 to 75 years of age, inclusive, at the time of signing the informed consent.

Type of Participants and Disease Characteristics

3. Patients with a definite diagnosis of AIH (type 1, 2 and 3) as per simplified or revised original diagnostic criteria (including response to CCSs) ([Hennes et al 2008](#)).
4. Patients who have been in biochemical remission (complete normalization of serum transaminases and IgG levels [*if IgG is measured, as according to local practice*]) for ≥ 2 years (*or less if according to the local practice*) prior to randomization. At least two measurements of IgG levels within normal range at least two weeks apart need to be available before randomization.
5. Patients who have been on stable treatment (CCSs \pm NSIs) for at least 3 months prior to randomization *and who have not had a dose increase in the previous 6 months prior to randomization*.
6. No signs of liver inflammation (HAI ≤ 3) on a liver biopsy taken no more than 12 months prior to randomization.
7. Patients with AIH who have previously not attempted (*or not attempted in the last 3 years, if this is the local practice*) to taper CCS to 0 mg/day.

Weight

8. Body mass index (BMI) within the range of 18-35 kg/m² (inclusive).

Sex and Contraception/Barrier Requirements

9. Male and female participants are eligible.

The contraception and abstinence requirements are intended to prevent exposure of an embryo to the study treatment. Therefore, the reliability of sexual abstinence for female enrollment eligibility needs to be evaluated in relation to the duration of the clinical study and the preferred and usual lifestyle of the participant. Periodic abstinence (e.g., calendar, ovulation, symptothermal, or post-ovulation methods) and withdrawal are not acceptable methods of preventing drug exposure.

A female participant is only eligible to participate if she is not pregnant, not breastfeeding, and at least one of the following conditions applies:

- Women of non-childbearing potential (WONCBP),

OR

- Women of childbearing potential (WOCBP), who:

Agree to remain abstinent (refrain from heterosexual intercourse) or use at least one acceptable contraceptive method during the treatment period and for at least 28 days after the final dose of study treatment.

The following are acceptable contraceptive methods: bilateral tubal occlusion/ligation, male sexual partner who is sterilized, established proper use of hormonal contraceptives that inhibit ovulation, hormone-releasing intrauterine devices and copper intrauterine devices, male or female condom with or without spermicide; and cap, diaphragm, or sponge with spermicide (see [Appendix 5](#)).

5.2 EXCLUSION CRITERIA

Participants are excluded from the study if any of the following criteria apply:

Medical Conditions

1. Patients with cirrhosis (F4 fibrosis by Fibroscan®) with significant impairment of liver function (Child Pugh category B or C).
2. Any other autoimmune disease (including overlap syndrome) requiring immunomodulating treatment.
3. History of infection with hepatitis B (HBsAg positive and/or anti-HBc positive; HBV vaccinated patients are eligible), human immunodeficiency virus (HIV; positive HIV antibody test), active hepatitis C virus (HCV) infection (detectable HCV RNA), detection of replicating CMV or Epstein-Barr virus (EBV).
4. Active infections requiring systemic therapy with antibiotic, antiviral, or antifungal treatment or febrile illness within 7 days before Day –1.
5. History of primary or acquired immunodeficiency.
6. Female patients: Pregnant or lactating.
7. Symptomatic herpes zoster within 3 months prior to screening.
8. History of active or latent tuberculosis or a positive Quantiferon® Gold test.
9. History of clinically significant severe drug allergies, multiple drug allergies, allergy to any constituent of the product, or intolerance to topical steroids.
10. Lymphoma, leukemia, or any malignancy within the past 5 years, except for basal cell or squamous epithelial carcinomas of the skin that have been resected with no evidence of metastatic disease for 3 years and in situ carcinoma of the cervix that was completely removed surgically. Breast cancer within the past 10 years.
11. Significant uncontrolled comorbidity, such as cardiac (e.g., moderate to severe heart failure New York Heart Association [NYHA] Class III/IV), pulmonary, renal, hepatic, endocrine, or gastrointestinal disorders (excluding UC).
12. Any condition or disease detected during the medical interview/physical examination that would render the patient unsuitable for the study, place the patient at undue risk, or interfere with the ability of the patient to complete the study in the opinion of the Investigator.

Prior/Concomitant Therapy

13. CCSs of < 5 mg/day (prednisolone-equivalent dose), or < 2.5 mg CCSs (prednisolone-equivalent dose) plus immune suppressant, or < 3 mg/day budesonide with or without immune suppressant.
14. CCSs > 20 mg/day (prednisolone-equivalent dose) or > 9 mg/day budesonide.
15. NSI daily dose higher than recommended standard of care therapy.
16. T or B cell-depleting therapy (e.g., rituximab) within the last 12 months or T- or B-cell number below normal due to depleting therapy.

Prior/Concurrent Clinical Study Experience

17. Leukocyte apheresis within 12 weeks of screening.
18. Donation of blood or blood products in excess of 500 mL within 3 months prior to screening.
19. Exposure to any investigational treatment within 6 months prior to Day 1.

Laboratory Abnormalities

20. Abnormal hematologic values:
 - Anemia (hemoglobin < 9 g/dL)
 - Leukocytosis (white blood cells $\geq 2 \times$ upper limit of normal [ULN])
 - Thrombocytopenia (platelet count < 100,000/ μ L)
 - Thrombocytosis (platelet count $\geq 2 \times$ ULN)
 - Eosinophilia (eosinophil count $\geq 2 \times$ ULN)
21. Abnormal hepatic enzyme or hepatic function values:
 - ALT, AST, or alkaline phosphatase, above normal range
 - Total bilirubin $\geq 2 \times$ ULN
 - International normalized ratio (INR) ≥ 1.7
 - Albumin < 3 g/dL
22. Abnormal biochemistry values:
 - IgG above normal range

Other Exclusions

23. History of regular alcohol consumption within 2 months of screening defined as:
An average weekly intake of > 14 drinks for men or > 7 drinks for women. One drink is equivalent to 12 g of alcohol: 12 ounces (360 mL) of beer, 5 ounces (150 mL) of wine, or 1.5 ounces (45 mL) of 80 proof distilled spirits (equivalent to 40 vol%).
24. Any suspicion or history of illicit drug use.

25. Patients under judicial supervision, guardianship, or curatorship.

5.3 LIFESTYLE CONSIDERATIONS

This section is not applicable for this study.

5.4 SCREEN FAILURES

Screen failures are defined as participants who consent to participate in the study but are not subsequently randomized to study treatment/entered in the study. Screen failures may be tracked separately.

The Investigator will maintain a screening log to record details of all participants screened and to confirm eligibility or record reasons for screening failure.

Individuals who do not meet the criteria for participation in this study (screen failure) may be re-screened up to three times if it is thought that the reason for failure is transient in nature.

Re-screened participants should be assigned the same participant number as for the initial screening.

For re-screened participants, the following specific criteria must be met:

- Results of a liver biopsy taken within 12 months of randomization must be available (see criteria for biopsy under Section 4.2.3).
- Testing for HBV, HIV, HCV, CMV, and EBV and latent tuberculosis infection need not be repeated if they have been already done within 6 months and their results were negative.
- WOCBP must repeat pregnancy testing.
- Screening laboratory evaluations beyond those itemized above must be completed within 28 days of the first dosing.

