8.11 TIMING OF STUDY ASSESSMENTS

8.11.1 Screening and Pre-treatment Assessments

Written informed consent for participation in the study must be obtained before performing any study-specific screening tests or evaluations. Informed Consent Forms (ICFs) for enrolled participant and for participants who are not subsequently enrolled will be maintained at the study site.

All screening, and all pre-treatment assessments (related to entry criteria), must be completed and reviewed to confirm that participants meet all eligibility criteria. The Investigator will maintain a screening log to record details of all participants screened and to confirm eligibility or record reasons for screening failure.

An Eligibility Screening Form documenting the Investigator's assessment of each screened participant with regard to the protocol's inclusion and exclusion criteria is to be completed by the Investigator and kept at the investigational site.

Screening and pre-treatment assessments will be performed within 28 days prior to Day 1, unless otherwise specified.

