Appendix 4 Clinical Laboratory Tests

The tests detailed in [Table 1](#) will be performed by the central laboratory with the exception of urinalysis, pregnancy testing, urine drug screen, and alcohol test. If the local laboratory results are used, the results must be captured in source documentation and entered into the eCRF.

Local laboratory results are only required in the event that the central laboratory results are not available in time for either study treatment administration and/or response evaluation. If a local sample is required, it is important that the sample for central analysis is obtained at the same time. Additionally, if the local laboratory results are used to make either a study treatment decision or response evaluation, the results must be captured in source documentation and entered as a comment into the eCRF.

Protocol-specific requirements for inclusion or exclusion of participants are detailed in Sections [5.1](#) and [5.2](#), respectively, of the protocol.

Additional tests may be performed at any time during the study as determined necessary by the Investigator or required by local regulations.

Table 1 Protocol-Required Safety Laboratory Assessments

Laboratory Assessments	Parameters
Hematology	
 Leucocytes, erythrocytes, hemoglobin, hematocrit, platelets, differential count (neutrophils, eosinophils, basophils, monocytes, lymphocytes).
Blood Chemistry	
 Sodium, potassium, chloride, CRP, bicarbonate, non-fasting glucose, urea, creatinine, creatine kinase (CK), protein, albumin, phosphate, calcium, total and direct bilirubin, alkaline phosphatase, ALT, AST, urate, GGT, IgG, IgA, IgM (IgA and IgM at screening, week 25, every 24 weeks thereafter and at early termination/end of study). Cholesterol, LDL cholesterol, HDL cholesterol, triglycerides.
Coagulation	
 Prothrombin time (i.e., INR) and activated thromboplastin time (aPTT).
Viral Testing	
 Serology: HIV (specific tests HIV-1 antibody, HIV-1/2 antibody, HIV-2 antibody), hepatitis B surface antigen (HBsAg), total hepatitis B core antibody (HBcAb) PCR: HCV, EBV and CMV
Hormones	
 Free T4, TSH Follicle-stimulating hormone (FSH) in females
IRR sample	
 IgE, tryptase (and includes exploratory safety biomarkers, see Section 8.2.5).

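### For re-screened patients only, Section 5.4 accepts a CMV/EBV PCR up to 6 months old for a criterion about current replication, while the other re-screening laboratory tests must be within 28 days of dosing

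*Combined protocol and SAP*

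**What the plan says.** Exclusion criterion 3 (Section 5.2, repeated in the synopsis) combines several infection criteria. For CMV and EBV the ground for exclusion is "detection of replicating CMV or Epstein-Barr virus (EBV". No time window is attached. Appendix 4, Table 1 lists the method as "PCR: HCV, EBV and CMV", and serology for HIV and hepatitis B.

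For first-time screening, Section 8.11.1 sets the window: "Screening and pre-treatment assessments will be performed within 28 days prior to Day 1, unless otherwise specified".

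Section 5.4 governs re-screening. A patient "may be re-screened up to three times if it is thought that the reason for failure is transient in nature". For that patient, the tests for HBV, HIV, HCV, CMV, EBV and latent tuberculosis "need not be repeated if they have been already done within 6 months and their results were negative". The same list ends: "Screening laboratory evaluations beyond those itemized above must be completed within 28 days of the first dosing".

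Among the tests that must be fresh are those behind exclusion 21 ("ALT, AST, or alkaline phosphatase, above normal range") and exclusion 22 (IgG above normal).

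**The concern.** A PCR result describes the day on which the blood was taken. Exclusion 3 asks whether CMV or EBV is replicating, which is a question about the patient's present state, and a negative result from months before does not answer it. The candidates are on corticosteroids with or without other immunosuppressants. Section 5.4 nevertheless lets CMV and EBV share the carry-over given to serological tests, and it holds routine chemistry to a much tighter limit. Two patients can thus meet the same criterion on evidence of very different age, and the protocol gives no reason for the difference.

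The main stake is eligibility and safety at entry. Section 2.3 lists immunosuppression from expanded regulatory T cells among the potential risks and says that adding the study drug to corticosteroids might in theory raise the risk of infection. A patient with unrecognised viral replication is one whom exclusion 3 was written to keep out.

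**Working it through.** No design figure bears on this point, so the check compares the rules and the age of result that each allows.

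**1. Criterion, test and oldest acceptable result**

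| Criterion | What excludes | Test | First screening | Re-screening |
|---|---|---|---|---|
| CMV, EBV (excl. 3) | replicating virus detected | PCR | 28 days | 6 months |
| HCV (excl. 3) | detectable RNA | PCR | 28 days | 6 months |
| HBV, HIV (excl. 3) | positive antigen or antibody | serology | 28 days | 6 months |
| Latent tuberculosis (excl. 8) | history or positive test | Quantiferon | 28 days | 6 months |
| ALT, AST, alkaline phosphatase, IgG (excl. 21, 22) | above normal | chemistry | 28 days | 28 days |

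The sources are Sections 5.2, 5.4 and 8.11.1, the Schedule of Activities and Appendix 4. The first three rows show that tests of current viral presence and tests of past or chronic infection share one waiver.

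**2. Age of the PCR at first dose**

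The biopsy item in Section 5.4 counts to randomization and the laboratory item counts to first dosing. The viral-test item names no date. Taking a month as 30 days:

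- 6 months counted back from first dose: 6 × 30 = 180 days, which is 180 / 28 = 6.4 times the limit for other laboratory tests.
- 6 months counted back from the start of re-screening, plus a full screening period: 180 + 28 = 208 days, or about 7 months.

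**3. What still protects a re-screened patient**

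- Exclusions 21 and 22 need fresh results, so replication that already raises ALT or AST is caught.
- Exclusion 4 removes patients with an active infection that needs systemic therapy, or with febrile illness in the 7 days before Day -1.
- Exclusion 12 covers any unsuitable condition found at interview or examination.
- The waiver applies only to a prior negative result, and it permits a repeat test without requiring one.

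What passes through is a re-screened patient with a negative PCR more than 28 days old in whom virus is now replicating, with normal enzymes, no recent fever, no treated infection and nothing found at examination. Because the sponsor lists CMV and EBV replication separately from enzyme elevation, it did not treat normal enzymes as a substitute for the PCR.

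**4. How many patients**

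The documents give neither a re-screening rate nor a rate of CMV or EBV replication, so the number cannot be derived. The following shows scale only, and both rates are assumptions:

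- Re-screened share of 10% to 30% of 84: about 8 to 25 patients exposed to the waiver.
- Missed replication in 1% to 5% of those: 8 × 0.01 = 0.08 to 25 × 0.05 = 1.25 patients.
- In the 7.5 mg and placebo arms (two of three): 0.08 × 2/3 = 0.05 to 1.25 × 2/3 = 0.83 patients.

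Under these assumptions the figures err on the high side, because not every re-screened patient would rely on a PCR older than 28 days.

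**The case against.** The strongest reply is that this is a deliberate exception. Section 8.11.1 allows other windows where specified, Section 5.4 specifies one, and exclusion 3 sets no recency limit. Formally there is no contradiction. That stands, but it does not explain why evidence of current replication may be more than six times as old as evidence on ALT.

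A second reply is that a patient who first failed because of a CMV or EBV illness would probably have had a positive PCR then, and the waiver needs a negative one. This also stands. The gap needs a PCR drawn before the illness, or an infection or reactivation arising between the two screenings. Section 5.4 does not list infection as a re-screening reason; it refers only to transient reasons.

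A third is that separating CMV and EBV from HCV is arbitrary, because HCV is also excluded on detectable RNA and tested by PCR. That is fair, and the fix below takes it into account.

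Two stronger readings are tempting, and the documents do not support them.

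- A reader might infer that exclusion 3 is not enforced. First-time screening applies it within 28 days, and at re-screening it still operates on a dated negative result with the other exclusions around it.
- A reader might infer a measurable threat to the primary endpoint, since Table 8 has no step to rule out a viral cause of an ALT rise. One such event would be 1/30 = 3.3% of the events in the primary comparison, but that only expresses one hypothetical event as a fraction and says nothing about how often it occurs. The missing attribution step affects every participant, including those with a fresh negative PCR who acquire or reactivate virus later, so a newer baseline PCR would not cure it. An initial ALT from 2 to below 5 × ULN must also persist on retest. The viral-testing row of the Schedule of Activities carries a second mark in a late column whose alignment is lost in the text available, so testing at or near relapse can be neither confirmed nor ruled out.

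**Conclusion.** The point holds as a narrow inconsistency in the eligibility rules. Only re-screened patients are affected, and only for criteria that depend on a current PCR result. The allowable age of that result is about 180 to 208 days, depending on an unstated reference date, against 28 days for first-time screening and for the other re-screening laboratory tests. The remaining exposure is replication with normal enzymes and no recent febrile or treated illness. The number affected cannot be computed from the documents. It is probably small: about one patient or fewer under the assumed rates shown above. No effect on power or on the hazard ratio is claimed. The case for acting rests on the very low cost of aligning the windows, not on a demonstrated harm. How Table 8 should classify ALT rises that are not due to AIH is a separate question.

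**What to change.** Reconcile Sections 5.2 and 5.4:

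- Take CMV and EBV PCR out of the 6-month waiver, so that they fall under the 28-day window that Section 5.4 already applies to other laboratory tests.
- Treat HCV RNA the same way for consistency, or state why it may stay under the waiver.
- For the tests that remain (HBV, HIV, latent tuberculosis), state the date from which the 6 months run, as the biopsy and laboratory items in the same list already do.

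This changes one list item and adds a reference date. The PCRs are already in the screening panel, and blood is drawn at re-screening anyway, so no visit is added. The downside is a few repeat PCRs and possibly a few more screen failures in a rare disease.
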